**GLOSSARY AND ABBREVIATIONS**

ICH GCP	International Conference on Harmonisation Good Clinical Practice
CFR	Code of Federal Regulations
IND	Investigational New Drug
IDE	Investigational Device Exemption
IRB	Institutional Review Board
DOR	Diminish ovarian reserve
DPOS	Dydrogesterone-primed ovarian stimulation
PPOS	Progesterin-primed ovarian stimulation
IVF	In vitro fertilization
ART	Assisted reproductive technology
FET	Frozen embryo transfer
RCT	Randomized clinical trial
ICSI	Intra Cytoplasmic Sperm Injection
DYG	Dydrogesterone
MIP	Microzined progesterone
MPA	Medroxyprogesterone acetate
AE	Adverse event
SAR	Serious adverse event
NATIONAL DI & ADR CENTRE	National centre of Drug information and adverse drug reactions monitoring
RTAC	Reproductive Technology Accreditation Certification
OHSS	Ovarian hyperstimulation syndrome

**SUMMARY OF CHANGES FROM PREVIOUS VERSION:**

Changed sections	Previous version: Protocol version 2.1	Update version: Protocol version 3.0	Reason of change from earlier version
Study Population	
Inclusion criteria:
 
 
• Women's age between 18 and 37 years
 
• AFC <math>\leq 5</math> and/or AMH <math>\leq 1.2</math> ng/ml
 
• Agree to perform single frozen blastocyst embryo transfer
 
 
Exclusion criteria:
 
 
• Oocyte recipient
 
• Indication of preimplantation genetic testing
 
• Known allergic reactions to medications in the Study (progesterone products, GnRH antagonist....)
 
• Basal FSH above 15mIU/mL.
 
• Have contraindications of ART treatment (e.g. critical or acute diseases)
 
• Retrieved sperm
 
• Repeated Implantation failure (had more than three failed embryo transfers with good quality embryos)
 
• Inability to comply with the study procedures
 
	
Inclusion criteria:
 
 
• Women's age between 18 and 37 years
 
• AFC <math>\leq 5</math> and/or AMH <math>\leq 1.2</math> ng/ml
 
• Agree to perform single frozen blastocyst embryo transfer
 
 
Exclusion criteria:
 
 
• Oocyte recipient
 
• Indication of preimplantation genetic testing
 
• Known allergic reactions to medications in the Study (progesterone products, GnRH antagonist....)
 
• Basal FSH above 15mIU/mL.
 
• Have contraindications of ART treatment (e.g. critical or acute diseases)
 
• Retrieved sperm
 
• Repeated Implantation failure (had more than three failed embryo transfers with good quality embryos)
 
• Inability to comply with the study procedures
 
• Patients with a history of thyroid cancer who are on hormone replacement therapy or those diagnosed with thyroid diseases at the time of eligibility assessment
 
	
After the SAE case related to thyroid cancer, DSMB and IRB have reviewed and stated that current evidence suggests the strong possibility that there is no link between the treatment being used in the trial and thyroid cancer.
 
To reduce any possible risk for current and prospective participants with thyroid disease in the study, the DSMB and IRB recommended that it should be excluded participants with current indications of thyroid diseases.
 
We update the exclusion criteria according to the recommendations.

Study Duration	Estimated Study Start Date (First patient in): April, 2023	Study Start Date (First patient in): June, 22th, 2023	- As of August 22, 2024, the study has pre-screened

Changed sections	Previous version: Protocol version 2.1	Update version: Protocol version 3.0	Reason of change form earlier version
	
Estimated Primary Completion Date (Last patient in): April, 2025
 
Estimated Study Completion Date: April, 2026
	
Estimated Primary Completion Date (Last patient in): May, 2027
 
Estimated Study Completion Date: December, 2027
	
2364 patients, of which 2071 patients failed pre-screening, 293 patients were screened, and 272 patients were recruited.
 
 
- The pre-screening failure rate is high, so to ensure the recruitment of the approved number of 730 patients, the research team requested an extension of the study period to December 2027.
 
- For the difficulties in recruiting patients into the study and slow recruitment progress, we have updated study timeline.
 
- We also update Study Start Date was June, 22th 2023, which was actually later than the initial estimated date (April 2023) for two months.
 

Visit 12	
Visit 12: (Day 163 ± 7 – Clinical pregnancy confirmation): A transvaginal ultrasound examination will be performed to determine the pregnancy defined as the presence of fetal heartbeats at gestation week 7 ± 1.
	
Visit 12: (Day 163 ± 7 – Clinical pregnancy confirmation): A transvaginal ultrasound examination will be performed to determine the pregnancy defined as the presence of at least one gestational sac at gestation week 7 ± 1.
	
Update typo error on page 16 of 46 - Visit 12

## **1. STATEMENT OF COMPLIANCE**

The trial will be conducted in accordance with the International Conference on Harmonisation Good Clinical Practice (ICH GCP), applicable Vietnamese Code of Federal Regulations (CFR), Terms and Conditions of Award. The Principal Investigator will assure that no deviation from, or changes to the protocol will take place without prior agreement from the Investigational New Drug (IND) or Investigational Device Exemption (IDE) sponsor, funding agency, and documented approval from the Institutional Review Board (IRB), except where necessary to eliminate an immediate hazard(s) to the trial participants. All personnel involved in the conduct of this Study have completed Human Subjects Protection and ICH GCP Training.

The protocol, informed consent form(s), recruitment materials, and all participant materials will be submitted to the IRB for review and approval. Approval of both the protocol and the consent form must be obtained before any participant is enrolled. Any amendment to the protocol will require review and approval by the IRB before the changes are implemented in the Study. All changes to the consent form will be IRB approved; a determination will be made regarding whether a new consent needs to be obtained from participants who provided consent, using a previously approved consent form.

## **2. PROTOCOL SUMMARY**

### **2.1. Summary**

One of the barriers in patients with diminished ovarian reserve (DOR) is the significantly reduced number of oocytes resulting in fewer oocytes collected and embryos formed. Many ovarian stimulation strategies have been proposed to improve oocyte or embryo quantity which is oocyte accumulation could be a potential option with a comparable success rate and reasonable cost. Dydrogesterone-primed ovarian stimulation (DPOS) protocol effectively blocks the Luteinizing hormone (LH) surge in IVF. It favors segment ART cycles such as FET, oocyte donor, fertility preservation, and oocyte accumulation set. The protocol is more user-friendly and cheaper than the GnRH antagonist regimen regarding LH suppression during ovarian stimulation. Initial evidence suggests that oocyte quantity and quality are comparable with other ovarian stimulation regimens. However, data related to the PPOS protocol has not been well documented. There has not been an RCT with a large sample size and well-designed to provide more substantial evidence. A randomized trial to compare the effectiveness of PPOS and GnRH antagonist protocol in IVF is urgently needed.

The randomized, open-label, multi-center trial will be conducted at IVFTA HCM – Tam Anh TP. Ho Chi Minh General Hospital and IVFTA HN – Tam Anh General Hospital, Vietnam. Patients will be randomized, using a computer-generated randomization list in a 1:1 ratio, to either the DPOS group or the GnRH antagonist group after assessing eligibility and signing informed consent. Randomization will be centrally controlled by a data scientist without involvement in any treatment procedure. After randomization, the patients will be administered human Menopausal Gonadotrophin (HMG) 225 IU/day (IU/d) via intramuscular injection on the 2nd - 4th menstrual day. In the intervention arm, women will receive oral Dydrogesterone 10mg (Duphaston 10mg) t.i.d daily from the first day of ovarian stimulation until final oocyte maturation. In the control arm, GnRH antagonist (Ganirelix 0.25mg) subcutaneously once daily from day 5 of ovarian stimulation will be administered till the day of final oocyte maturation. Oocyte cryopreservation will be applied to collect at least  $7 \pm 1$  oocytes. In the last ovarian

stimulation cycle, the fresh oocytes and all thawed oocytes will be fertilized by ICSI. The freeze-all strategy will be applied in both arms, and single blastocyst frozen embryo transfer will be performed in the next menstrual cycle.

The ongoing pregnancy rate of patients in IVFTA HCM was 45.0% in the Antagonist IVF stimulation group. To show or refute that hypothesis: no significant difference in ongoing pregnancy rates when using DPOS protocol (40 - 42%), we need 657 patients to produce a two-sided 95% confidence interval for the difference in population proportions with a width that is equal to 5% (margin = 5.0%, alpha = 5.0% and power = 80%). Considering a 10% loss to follow-up and protocol violation, we plan to recruit 730 participants (365 per arm). The primary endpoint is the ongoing pregnancy rate after the first completed transfer. Secondary endpoints are ovarian stimulation, embryo culture characteristics, drop-out rate, and DPOS and GnRH antagonist protocol safety.

All analyses will be performed on an intention-to-treat basis using the R statistical package

## 2.2. Synopsis

Title:	Dydrogesterone primed ovarian stimulation versus fixed gonadotropin-releasing hormone antagonist protocol for accumulation of oocyte in patients with low ovarian reserve: A randomized controlled trial
Objectives:	Primary objective:  To compare the ongoing pregnancy rate per patient in low ovarian reserve patients after accumulation oocyte cycles with either dydrogesterone primed ovarian stimulation (DPOS) or gonadotropin-releasing hormone antagonist (GnRHanta) protocol
	Secondary objectives:  1. To compare the characteristics of ovarian stimulation between DPOS and GnRHanta protocol, including LH, Estradiol, and Progesterone profile (Day 1, day 5, and day 8 of ovarian stimulation, final oocyte maturation day, and 12 hours after the final oocyte maturation injection), premature LH rate, the duration of ovarian stimulation the total dose of FSH and the number of ovarian stimulation cycles. 2. To compare the outcomes of the ovarian stimulation between DPOS and GnRHanta protocol, including number of cumulus-oocyte complexes, number of MII oocytes, oocyte survival rate, fertilization rate, embryo-cleavage rate, blastocyst rate, top-quality blastocyst rate, blastocyst survival rate, implantation rate, positive pregnancy rate, clinical pregnancy rate, early miscarriage rate, multiple pregnancy rate, ectopic pregnancy rate. 3. To compare the drop-out rate of DPOS and GnRHanta protocol in accumulation oocyte cycles of patients with low ovarian reserve

4. To assess the safety of DPOS and GnRHanta protocol in accumulation oocyte cycles of patients with low ovarian reserve.
5. To compare the quality of life during ART treatment based on the WHO-BRIEF questionnaire

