### Screening and Enrollment

- **Visit 2** (Day 1: the first day of OS cycle - Ovarian stimulation (OS) starts on the 2nd – 4th of mense):
  - The patients undergo a transvaginal ultrasound to access Antral Follicle Count, ovaries and uterus.
  - Laboratory tests (blood tests, urine test and ECG) will be taken for pre-anesthesia examination; in addition, the hormone values include FSH (follicle-stimulating hormone) – only for the first OS cycle, E2 (Estradiol), LH (luteinizing hormone), P4 (Progesterone) and AMH if the result is not

available within 6 months. A pre-anesthesia examination will ensure the patient is eligible for the oocyte retrieval procedure.

- Screening for eligibility will be performed by treating physicians.
- Eligible participants will be invited to a full discussion with investigators about the Study and given the informed consent form. Patients will be given a period (3-4 hours) during anesthesia testing to understand the information and decide whether they agree to participate in the Study. The investigators will obtain written informed consent from all couples before enrolment. To maximize retention in the trial, a consultation will be available to couples to ensure they understand the procedures well and to address any questions or complaints that arise during the Study.

**Treatment period:** The patient will be treated with an oocyte accumulation strategy, and estimated ovarian stimulation cycles range from two to four cycles to collect at least  $7 \pm 1$  oocytes.

*For the first ovarian stimulation cycle:*

- **Visit 2** (Day 1: the first day of OS cycle - Ovarian stimulation (OS) starts on the 2nd – 4th of mense): After informed consent is obtained, the patient will be indicated randomly with one of the following regimens:

**Group I:** oral DYG (Duphaston) 10mg t.i.d from the first day of OS to the day of final oocyte maturation

**Group II:** GnRH antagonist (Ganirelix 0.25 mg) will be initiated on the fifth day of OS to the day of final oocyte maturation

- **Visit 3** (1st cycle - Day 5 of OS): Transvaginal ultrasound and blood sampling (for hormone check-up) will be performed.
- **Visit 4** (1st cycle - Day 8 of OS): Transvaginal ultrasound and blood sampling (for hormone check-up) will be performed.
- **Visit 5** (1st cycle - Day  $10 \pm 2$  of OS): Transvaginal ultrasound and blood sampling (for hormone check-up) will be performed. A final oocyte maturation injection will be performed.

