- **Visit 6** (1st cycle - Day  $11 \pm 2$  of OS): blood sampling (for hormone check-up) will be performed after 12 hours of final oocyte maturation injection.
- **Visit 7** (1st cycle - Day  $12 \pm 2$  of OS): Oocyte retrieval and oocyte cryopreservation will be performed. AE/SAE will be recorded routinely.

*For the following ovarian stimulation cycle (s):* the patient will be stimulated with the previous OS protocol. The visits of the patient will be repeated as the first OS cycle.

*For the last ovarian stimulation cycle:* Based on the aim to collect at least  $7 \pm 1$  oocytes, the clinician will determine the last ovarian stimulation cycle on the day of final oocyte maturation. It is defined as a cycle in that the total number of frozen and expected fresh oocytes are at least  $7 \pm 1$  oocytes. The patient will be stimulated with the

previous OS protocol. The visits of the patient will be repeated as the first OS cycle. However, the frozen oocytes of the previous OS cycle will be thawed. All fresh and thawed oocytes will be fertilized by ICSI at **Visit 7**.

- **Visit 8:** (Day 77 ± 7 – Embryo culture report): The patient will receive a Blastocyst embryo culture report and decide whether embryo cryopreservation or not.
- **Visit 9:** (Day 90 ± 7 – Endometrial preparation): Endometrial preparation will start on the 2nd – 4th of mense.
- **Visit 10:** (Day 109 ± 7 – Embryo transfer): Progesterone will be started when endometrial thickness reaches 8 mm or more for 6 - 7 days. Embryo transfer will be performed under ultrasound.
- **Visit 11:** (Day 121 ± 7): On day 11, after embryo transfer, subjects will have a routine pregnancy test (serum β-hCG) to confirm the subject's biochemical pregnancy
- **Visit 12:** (Day 163 ± 7 – Clinical pregnancy confirmation): A transvaginal ultrasound examination will be performed to determine the pregnancy defined as the presence of at least one gestational sac at gestation week 7 ± 1 .
- **Visit 13** (Day 198 ± 7 - End of treatment): A transvaginal ultrasound examination will be performed to determine the Ongoing pregnancy, defined as fetal heartbeats at gestation week 12 ± 1 .

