### 6.2. Exclusion criteria

- Oocyte recipient
- Indication of preimplantation genetic testing
- Known allergic reactions to medications in the Study (progesterone products, GnRH antagonist....)
- Basal FSH above 15mIU/mL.
- Have contraindications of ART treatment (e.g. critical or acute diseases)
- Retrieved sperm
- Repeated Implantation failure ( ≥ 3 failed embryo transfers with good-quality embryos)
- Inability to comply with the study procedures.
- Patients with a history of thyroid cancer who are on hormone replacement therapy or those diagnosed with thyroid diseases at the time of eligibility assessment

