## 7.2. Screening and Enrollment

The patients will be checked for inclusion criteria on the second - fourth menstrual day (Visit 2). Laboratory tests (blood tests, urine test and ECG) will be taken for pre-anesthesia examination; in addition, the hormone values include FSH (follicle-stimulating hormone) – only for the first OS cycle, E2 (Estradiol), LH (Luteinizing hormone), P4 (Progesterone) and AMH if the result is not available within 6 months. A pre-anesthesia examination will be performed to ensure that the patient is eligible for the oocyte retrieval procedure.

On the day (Visit 2), screening for eligibility will be performed by treating physicians. If the patients are eligible, we will invite them to a full discussion about the Study and give the informed consent form. We will inform verbal and written consent and explain the relevant information such as study context, objectives, and data collection procedure. Patients will be given a period (3-4 hours) during anesthesia testing to understand the information and decide whether they agree to participate in the Study. The investigators will obtain written informed consent from all couples before enrolment. To maximize retention in the trial, a consultation will be available to couples to ensure they understand the procedures well and to address any questions or complaints that arise during the Study.

When there is an eligible participant to be enrolled in the Study, clinicians from the specific site will enter the study data management center to get the allocation of patients according to a computer-generated randomization list in a 1:1 ratio, with a variable block size of 2, 4, 6 or 8. After randomization, if a participant wishes to change her assigned protocol in the first cycle, she will be considered a crossover but analysed in the group she was assigned (intention-to-treat). However, if she wishes to change the assigned protocol from the second ovarian stimulation cycle or transfer more than one embryo after randomization, it will be considered a protocol violation and excluded from the analysis. Due to the type of interventions, this Study will be label-opened to clinicians who perform ovarian stimulation, oocyte retrieval, and embryo transfer.

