## 8. OUTCOME MEASUREMENTS

The primary endpoint is ongoing pregnancy after the first embryo transfer. Ongoing pregnancy is defined as pregnancy with a detectable heart rate at 12 weeks' gestation or beyond after the completion of the first transfer. Cycles in which no blastocyst is available for transfer will be considered failures. Several fertility outcomes, characteristics, and outcomes of the ovarian stimulation, patient safety, drop-out rate, and quality of life during oocyte accumulation will be assessed as secondary endpoints. Full details and definitions are provided in Table 2.

**Table 2.** Secondary endpoints and their definition

Secondary endpoints	Definition
LH, Estradiol and progesterone profile	LH, Estradiol, and progesterone level are measured on day 1, day 5, and day 8 of ovarian stimulation, final oocyte maturation day, and 12 hours after the final oocyte maturation injection
Rate of premature LH surge	Premature LH surge (PLS) is increased serum LH more than twice the baseline or more than 15 mIU/ml

	The rate of Premature LH surge is defined as number of PLS appearances per number of ovarian stimulation cycles
Duration of ovarian stimulation	Number of ovarian stimulation days (from the first day of FSH injection to final oocyte maturation injection day)
The total dose of FSH	A number of international units of HMG are administrated during ovarian stimulation
Number of Cumulus-oocyte complex (COCs)	Number of Cumulus-oocyte complexes after oocyte retrieval
Number of MII oocyte	Number of MII oocytes after denuding
Number of survival oocyte	Number of survival oocytes after thawing
Fertilization rate per oocyte inseminated/injected	Fertilisation is defined as the appearance of two PN at 17±1 hour per inseminated/injected
Embryo-cleavage rates	Number of embryos on Day 3 after ICSI day
Blastocyst rate	Numbers of embryos on Day 5 and Day 6 after ICSI
Number of survival blastocyst	Number of survival embryos on Day 5 and Day 6 after thawing
Top-quality blastocyst rate	Numbers of embryos on Day 5 and Day 6 with good quality after ICSI
Positive pregnancy test	A positive pregnancy test is defined as a serum hCG level greater than 25 mIU/mL 11 days after the first transfer
Implantation rate	Implantation rate is defined as the number of gestational sacs per number of embryos transferred 3 weeks after the first transfer
Biochemical pregnancy	Biochemical pregnancy is defined as a pregnancy diagnosed only by the detection of beta hCG in serum or urine

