#### *12.3.3. Secondary outcome*

For continuous variables, results will be shown as mean (SD) and between-group differences will be considered using Student's t-test. For dichotomous outcomes, relative risk (RR) and 95% confidence interval (CI) values will be calculated.

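### First-cycle Day 1 LH, estradiol and progesterone are pre-randomisation baselines listed as between-arm endpoints, and the unadjusted t-test for the later values leaves them unused as a covariate

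*Protocol*

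**What the plan says.** The first secondary objective, in both the Synopsis (2.2) and Section 4.2, is a comparison between the two regimens of the "LH, Estradiol, and Progesterone profile (Day 1, day 5, and day 8 of ovarian stimulation, final oocyte maturation day", with a fifth sample 12 hours after the trigger. The Synopsis endpoint list repeats it, and Table 2 in Section 8 defines the endpoint as "LH, Estradiol, and progesterone level are measured on day 1, day 5, and day 8 of ovarian stimulation" and the two later times. None of these places separates Day 1 from the other times or calls it a baseline.

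Section 7.2 describes the Visit 2 laboratory work: "in addition, the hormone values include FSH (follicle-stimulating hormone) – only for the first OS cycle, E2 (Estradiol), LH (Luteinizing hormone), P4 (Progesterone". The restriction to the first cycle applies to FSH; the other three hormones are measured in every cycle. Section 6.2 excludes women with "Basal FSH above 15mIU/mL". Randomisation comes later in the same visit (Section 5): "After informed consent is obtained, the patient will be indicated randomly with one of the following regimens". For later cycles, Section 5 says "the patient will be stimulated with the previous OS protocol. The visits of the patient will be repeated as the first OS cycle".

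On analysis, Section 12.3.3 states: "For continuous variables, results will be shown as mean (SD) and between-group differences will be considered using Student's t-test". The only covariate adjustment in the protocol is in 12.3.2. It concerns the primary outcome, and only if the arms are prominently imbalanced.

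**The concern.** A value measured before allocation cannot be affected by allocation. Listing it among times at which the regimens are to be compared invites a significance test whose null hypothesis is true by design, so any result below 0.05 is a false one.

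The same value has a proper use that the protocol does not make of it. A woman's own pre-treatment LH, estradiol or progesterone may predict her later values. Where it does, adjusting for it sharpens the comparison at Day 5, Day 8, trigger day and 12 hours, and removes the effect of any chance imbalance at the start. At stake are the precision and clean reading of a secondary endpoint.

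**Working it through.** **Order of events in cycle 1.** Sections 5 and 7.2 describe Visit 2 in the same sequence: laboratory tests including FSH, LH, estradiol and progesterone; eligibility check; discussion and consent; randomisation; start of stimulation. The FSH result decides eligibility under 6.2, so it must be known before a woman can be randomised. LH, estradiol and progesterone are listed in the same set of tests. The schedule in 2.4 lists the hormones below the randomisation row, but it groups rows by stage within one visit and gives no order within the day. The reading that the first-cycle sample precedes randomisation and the first dose is therefore well supported.

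**Stated figure.** The protocol gives no power or precision for the hormone endpoints, so there is none to reproduce.

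**Testing the baseline.** Inputs: three hormones; two-sided 0.05 (Section 12.3). If all three first-cycle Day 1 values are tested and the tests are independent, the chance of at least one p < 0.05 is 1 − 0.95³ = 1 − 0.857 = 0.143. Correlation between the hormones would change this figure.

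**Gain from adjustment.** With r the correlation between the Day 1 value and a later value of the same hormone, ANCOVA multiplies the residual variance by 1 − r². The documents give no r; 0.2 to 0.5 is an assumption.

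| Assumed r | Variance factor 1 − r² | Reduction | Equivalent sample size 1/(1 − r²) | Power where the t-test has 80% |
|---|---|---|---|---|
| 0.2 | 0.96 | 4% | 1.04 | 82% |
| 0.5 | 0.75 | 25% | 1.33 | 90% |

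The last column is Φ[(1.96 + 0.8416)/√(1 − r²) − 1.96]. For r = 0.2 this is Φ(2.859 − 1.96) = Φ(0.899) = 0.82. For r = 0.5 it is Φ(3.235 − 1.96) = Φ(1.275) = 0.90.

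**Effect of a chance imbalance.** Suppose Day 1 happens to differ between arms at z = 1.96. The unadjusted t-test of a later value then has a conditional type I error of 1 − Φ[1.96(1 − r)/√(1 − r²)] + Φ[−1.96(1 + r)/√(1 − r²)].
- r = 0.2: 0.0548 + 0.0082 = 6.3%.
- r = 0.5: 0.1289 + 0.0003 = 12.9%.

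Averaged over all randomisations the error stays at 5%, so the t-test is valid; it is only less efficient and exposed to baseline luck.

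**The case against.** The best defence is that a hormone profile naturally begins at its starting value, that Table 2 only says when levels are measured, and that no sentence orders a separate Day 1 test. This stands in part: showing Day 1 beside the later times is ordinary reporting, and the premature-surge definition in Table 2 itself needs a baseline LH. But the stated objective is to compare the arms at the listed times, Day 1 among them, and 12.3.3 applies one test to all continuous secondary outcomes. Read as written, Day 1 is included.

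A second defence is that covariates for secondary endpoints are usually left to the statistical analysis plan, which Section 12.3 promises before data-lock. That would dispose of a complaint about silence. Here the protocol names a test, and the proposal is a specific improvement to it at no cost. It remains an improvement, not the repair of an invalid analysis.

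Four stronger inferences are not supported:
- **That the blood is drawn before consent.** Section 7.2 gives women 3 to 4 hours to decide while the anaesthesia testing is under way, so testing and consent overlap. Only precedence over randomisation is secure.
- **That Day 1 values are pooled over cycles, diluting a carry-over effect.** No section says they are pooled, and carry-over is not an objective.
- **That Day 1 of later cycles would be a sound randomised outcome.** Whether a woman enters another cycle depends on the oocytes already collected, a post-randomisation result.
- **That the t-test on later values inflates the error rate.** Unconditionally it does not.

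**Conclusion.** The point holds, and it is minor. First-cycle Day 1 LH, estradiol and progesterone are baselines placed in a between-arm endpoint, and the planned t-test does not use them to sharpen the comparisons that treatment can affect.

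The 14.3% applies only if three independent tests are run. The 4% to 25% variance reduction rests wholly on an assumed r of 0.2 to 0.5, and at the lower end the gain is small. That sampling precedes randomisation rests on the order of steps in Sections 5 and 7.2 and on the FSH criterion, since no single sentence states it. The primary outcome, the sample size and the interim stopping rule are unaffected.

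**What to change.** 1. In 2.2, 4.2 and Table 2, label first-cycle Day 1 LH, estradiol and progesterone as baseline and take them out of the between-arm comparison. Report them descriptively by arm without a p-value. This needs saying, because 12.3.1 as written would otherwise compare them by t-test or a non-parametric test as a patient characteristic.
2. In 12.3.3, replace the t-test for Day 5, Day 8, trigger-day and 12-hour values with a linear model (ANCOVA) containing arm and the first-cycle Day 1 value of the same hormone.
3. If Day 1 of later cycles is shown, report it separately and descriptively, with a note that it covers only women who needed another cycle. The same selection affects the other hormone values from those cycles, so the clean randomised comparison is in cycle 1.

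The cost is a few lines in the protocol or in the analysis plan before data-lock. No new data, visits or participants are needed.
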